1 INTRODUCTION

The purpose of this Statistical Analysis Plan (SAP) is to provide a description of the statistical methods to be implemented for the analysis of data from the study with protocol number H-100-002. The SAP will be finalized prior to database lock. Any deviations from the SAP after database lock will be documented in the final Clinical Study Report (CSR).

2 STUDY OVERVIEW

2.1 Study Objectives

2.1.1 Primary Objectives

- To assess the safety and reactogenicity of HB-101.
- To assess the immunogenicity of HB-101.

2.1.2 Secondary Objectives

- To assess the efficacy of the administration of at least 2 doses of HB-101 compared to that of placebo in mitigating CMV DNAemia/viremia for CMV seronegative (-) recipients awaiting kidney transplantation from a CMV seropositive (+) donor and followed by CMV preemptive therapy post-transplant.
- To assess the efficacy of the administration of at least 2 doses of HB-101 compared to that of placebo in decreasing the use of anti-virals at treatment dose for CMV seronegative (-) recipients awaiting kidney transplantation from a CMV seropositive (+) donor and to be treated prophylactically for CMV post-transplant.
- To assess the efficacy of the administration of at least 2 doses of HB-101 in CMV seropositive (+) recipients awaiting kidney transplant and followed by CMV post-transplant preemptive management or prophylactic anti-viral therapy.

2.1.3 Exploratory Objectives

To assess additional immunogenicity parameters of HB-101.

[figure not shown]
2.2 Study Design

2.2.1 Overview

This is a Phase 2 study of HB-101, a bivalent CMV vaccine, in patients awaiting kidney transplantation and includes a randomized, placebo-controlled portion (Groups 1 and 2) and an open-label portion (Group 3). Approximately 150 patients recruited globally from specified transplant centers will be enrolled. The study will occur at approximately 25 to 40 global sites.

A high-level study schematic of Study H-100-002 is presented in Figure 1.

Figure 1 High-Level Study Schematic

For Groups 1 and 2, adult CMV seronegative (-) patients awaiting kidney transplant from a CMV seropositive (+) living donor will be enrolled according to treatment intent with regard to the method of CMV prevention after transplant (either preemptive or prophylactic) as defined at study enrollment by the investigator and institutional standards.

Patients enrolled into Groups 1 and 2 should have a living donor kidney transplantation ideally planned between 2 to 4 months after the first injection of study drug (HB-101 or placebo).

- Group 1 - The preemptive group will be randomized in a 2:1 ratio (HB-101:placebo) to receive either HB-101 or placebo before transplant. Post-transplant patients will be monitored per preemptive institutional standards.
- Group 2 - The prophylactic group will be randomized in a 2:1 ratio (HB-101:placebo) to receive either HB-101 or placebo before transplant. Post-transplant patients will receive 3 to 6 months of anti-viral prophylaxis following institutional standards.

Enrollment of Group 2 will be limited to no more than 54% of total patients.

For Group 3, adult CMV seropositive (+) patients awaiting kidney transplant from a CMV seropositive (+) or CMV seronegative (-) living donor will be enrolled into Group 3. Post-transplant CMV management will follow either preemptive or prophylactic care as defined at study enrollment by the investigator and institutional standards.

Patients enrolled into Group 3 should have a kidney transplantation from a living donor planned between 2 to 4 months after the first injection of HB-101. Patients in Group 3 will receive HB-101 vaccination(s) prior to their transplant surgery. Enrollment of Group 3 will be a minimum of 15% of total patients.

Patients receiving at least 2 doses of study drug before transplant will be included in the statistical analysis of the efficacy endpoints.

The patient will complete and conclude the study on whichever day of the study one of the following events first occurs:

- When the patient completes the study follow-up (12 months post-transplant).
- If for some reason kidney transplant has not occurred by 12 months after the first dose of study drug (HB-101 or placebo).
- If the patient experiences graft failure requiring removal of the transplanted organ or returns to dialysis.
- If the patient is withdrawn or withdraws from the study.
- If the patient is lost to follow-up.
- If the patient dies.

The total duration of the study for each patient participating in the study will be approximately 15 months.

The dosing schedule relative to transplantation is listed in Table 1.

Study drug is defined as either HB-101 or placebo.

Table 1 Timing of Kidney Transplant vs. Study Drug (HB-101 or Placebo) Injection, Where Day 0 is the Day of First Dose of Study Drug

Timing of Kidney Transplant	Number of Injections Planned	Timing of Study Drug Injection
Prior to Day 34	1*	Day 0
Between Day 35 and Day 62	2	Day 0 and Day 28**
Between Day 63 and Day 90 or Between Day 91 and Day 120	3	Day 0, Day 28**, and Day 56** or Day 84**
*Patients who received only 1 dose of study drug will be excluded from the mITT Population for efficacy analysis. **After Day 0 dose administration, a timeframe of ± 7 days from scheduled day of dosing is allowed. mITT = modified Intent-to-Treat; Day 0 = day of first dose of study drug; Day 28 = 28 days after the first dose of study drug; Day 34 = 34 days after the first dose of study drug; Day 35 = 35 days after the first dose of study drug; Day 56 = 56 days after the first dose of study drug; Day 62 = 62 days after the first dose of study drug; Day 63 = 63 days after the first dose of study drug; Day 84 = 84 days after the first dose of study drug; Day 90 = 90 days after the first dose of study drug; Day 91 = 91 days after the first dose of study drug; Day 120 = 120 days after the first dose of study drug.		

In brief, it is the intent of this study to administer up to 3 doses of study drug (HB-101 or placebo) prior to transplantation and within proximity to the time of transplantation. However, 2 doses of study drug before transplant will be sufficient for the patients to be included in the efficacy analyses if a third dose of study drug is not feasible due to transplantation timelines. Patients will not receive study drug after transplantation.

After Day 0 dose administration, the subsequent study drug administration(s) should be given 28 days (± 7 days) apart.

Patients whose planned transplantation is less than 35 days from the planned first study drug (HB-101 or placebo) injection should not be enrolled.

A minimum of 7 days (± 2 days) must be planned between the last dose of study drug and transplantation, unless agreed otherwise between the sponsor and investigator on a case-by-case basis.

Patients whose planned transplantation is no longer than 4 months from the time of the first study drug (HB-101 or placebo) injection should be enrolled. Changes in transplantation timelines will not result in patient withdrawal from the study. In case of delayed transplantation, additional study drug injections prior to transplantation can be discussed with the sponsor or sponsor designee (who should be blinded). The maximum allowed number of patients receiving additional study drug injections prior to transplantation will be capped at 10 patients (less than 10% of planned sample size).

For Groups 1 and 2, in the event that the living donor is not available and a kidney from a CMV seropositive (+) deceased donor becomes available, the patient can continue in the study after transplantation. For Group 3, in the event that the living donor is not available and a kidney from a deceased donor becomes available, the patient can continue in the study after transplantation.

The additional study drug booster will be administered at least 7 days (± 2 days) prior to the scheduled transplantation. This allows maximal protection against CMV prior to the transplant. Blood collection for immunogenicity will be performed prior to each study drug booster

administered. Immunogenicity will not be used to determine the administration of a booster as these results would be unblinding; instead, reactogenicity will be reviewed and the investigator and sponsor may decide not to administer the booster if there is evidence of increasing reactions with increasing number of vaccinations. The number and timing of vaccinations versus transplantation will be described in the descriptive analyses.

The schedule of events and Immunogenicity analysis and time points are listed in Appendix A.

2.2.2 *Randomization and Blinding*

For groups 1 and 2, adult CMV seronegative (-) patients awaiting kidney transplant from a CMV seropositive (+) living donor will be enrolled into Groups 1 or 2 according to treatment intent with regard to the method of CMV prevention after transplant (either preemptive or prophylactic) as defined at study enrollment by the investigator and institutional standards.

- Group 1 - The preemptive group will be randomized in a 2:1 ratio (HB-101:placebo) to receive either HB-101 or placebo before transplant. Post-transplant patients will be monitored per preemptive institutional standards.
- Group 2 - The prophylactic group will be randomized in a 2:1 ratio (HB-101:placebo) to receive either HB-101 or placebo before transplant. Post-transplant patients will receive 3 to 6 months of anti-viral prophylaxis following institutional standards.

Patients will be randomized via a centralized Interactive Response Technology (IRT) system. Enrollment of Group 2 will be limited to no more than 54% of total patients.

The study is double-blind for Groups 1 and 2; patients and investigators will be blinded to treatment assignment.

Group 3 will be open label. In Group 3, CMV seropositive (+) patients awaiting kidney transplant from a CMV seropositive (+) or CMV seronegative (-) donor will be enrolled to receive HB-101 vaccination(s) prior to their transplant surgery. There will be no randomization or blinding for patients in Group 3. Enrollment of Group 3 will be a minimum of 15% of total patients.

Hookipa Biotech study team members may be unblinded after each patient receives their last dose of study drug and undergoes his/her kidney transplantation. Medpace, the investigator, and study site personnel will remain blinded for the entire study with the exception of the study site pharmacist or designee or research nurse at each site who prepares the study drug for blinded administration.

2.2.3 *Study Drug*

HB-101 uses replication-deficient lymphocytic choriomeningitis virus (rLCMV) as a vector for a bivalent recombinant vaccine against Human Cytomegalovirus (HCMV). One vector expresses the pp65 protein of HCMV, and one expresses a truncated glycoprotein B (gB) protein of HCMV. The 2 vectors are produced separately. The final drug product is manufactured by mixing 1 batch of rLCMV pp65 and 1 batch of rLCMV gB in a 1:1 ratio based on pp65- and gB-expressing vectors. HB-101 was produced pre-diluted and ready-to-use. HB-101 is formulated at 1.2×10^8 FFU/mL. The product is filled in 2 mL single-dose vials containing 0.7 mL of vaccine. Sodium chloride (0.9% w/v) will be used as the placebo. The sponsor will supply this saline for the study.

2.2.4 *Sample Size Determination*

A total sample size of approximately 150 patients is planned for the study. Patients in Groups 1 and 2 will be randomized with a 2:1 ratio for active versus placebo. Patients in Group 3 will be enrolled to receive open-label HB-101. The sample size has been set for an initial assessment of the safety and immunogenicity of the vaccine candidate, which will provide for approximately 100 patients exposed to the HB-101 vaccine. No formal statistical assessment for sample size determination has been conducted. The sample size is considered adequate to provide the necessary safety and immunogenicity data and help with the determination of point estimates of clinical efficacy endpoints (clinically significant CMV infection as defined by the Food and Drug Administration (FDA) "Guidance for Industry: Cytomegalovirus in Transplantation: Developing Drugs to Treat or Prevent Disease") to design and adequately statistically power Phase 3 trials.

2.3 Study Endpoints

2.3.1 *Primary Endpoints*

For objective of assessing the safety and reactogenicity of HB-101, the primary endpoints are

- Incidence and severity of Adverse events (AEs), serious adverse events (SAEs), and changes in laboratory values
- Incidence and severity of localized or generalized injection site reactions

For objective of assessing the immunogenicity of HB-101, the primary endpoints are descriptive central statistics of the following immunogenicity parameters:

- CMV Neutralization (neut)
- CMV Enzyme-linked immunospot (ELISPOT) phosphoprotein 65 Kd (pp65)
- CMV ELISPOT gB

2.3.2 *Secondary Efficacy Endpoints*

- Incidence and time to clinically significant CMV infection, CMV disease, and CMV syndrome after transplant
- Incidence and time to CMV viremia requiring anti-viral therapy after transplant
- Incidence and duration (in days) of anti-CMV therapy courses (at therapeutic doses) required after transplant
- Incidence and time to quantifiable CMV DNAemia , peak CMV DNAemia level, and duration of CMV DNAemia above the limit of quantitation after transplant
- Incidence and time to graft failure and organ rejection after transplant

2.3.3 *Exploratory Efficacy Endpoints*

Descriptive central statistics of the following immunogenicity parameters:

- CMV Intracellular cytokine staining (ICS) pp65
- CMV ICS gB
- LCMV ELISPOT nucleoprotein (NP)

3 STATISTICAL METHODOLOGY

3.1 General Considerations

3.1.1 Analysis and Study Days

Analysis day will be calculated from the date of kidney transplant. The day of kidney transplant will be Analysis Day 1, and the day immediately before Analysis Day 1 will be Analysis Day -1. There will be no Analysis Day 0.

Study Day may also be calculated based on the date of first dose of study drug. The day of the first dose of study drug will be Study Day 0, and the day immediately before Study Day 0 will be Study Day -1.

3.1.2 Definition of Baseline

Unless otherwise defined, baseline is defined as the last measurement prior to the first dose of study drug. Some analyses may also use the date of kidney transplant as the reference point for pre- and post-transplant analyses.

3.1.3 Summary Statistics

Continuous variables will be summarized by using the number of non-missing observations, arithmetic mean, standard deviation, median, minimum, and maximum values as descriptive statistics. Categorical variables will be summarized by using the frequency count and the percentage of patients in each category as descriptive statistics. All data will also be listed.

Within each population, results will be presented according to treatment arm and total for Groups 1 and 2 and open-label HB-101 for Group 3 and total for all the three groups unless specified otherwise. Results from Groups 1 and 2 and results from Group 3 will be displayed in separate outputs unless specified otherwise.

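### The SAP does not clearly require secondary efficacy results within Group 1 and within Group 2, although each group has its own placebo-controlled objective

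*SAP*

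**What the plan says.** Section 2.1.2 has two placebo-controlled secondary objectives for seronegative recipients. The first concerns CMV DNAemia/viremia in patients with a seropositive "donor and followed by CMV preemptive therapy post-transplant". The second concerns anti-viral use at treatment dose in patients with a seropositive "donor and to be treated prophylactically for CMV post-transplant". Sections 2.2.1 and 2.2.2 make these populations Groups 1 and 2 and randomise each 2:1. The third objective (Group 3, open label) has no placebo comparison.

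The two groups have different backgrounds after transplant. For Group 2, "Post-transplant patients will receive 3 to 6 months of anti-viral prophylaxis following institutional standards". Group 1 is monitored under preemptive standards. The post-transplant schedule in Appendix A has a separate row of local PCR testing for each strategy.

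On group sizes, 2.2.1 says: "Enrollment of Group 2 will be limited to no more than 54% of total patients" and "Enrollment of Group 3 will be a minimum of 15% of total patients". Nothing else fixes the mix.

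The general display rule in 3.1.3 presents results "according to treatment arm and total for Groups 1 and 2 and open-label HB-101 for Group 3 and total for all the three groups". It continues: "Results from Groups 1 and 2 and results from Group 3 will be displayed in separate outputs unless specified otherwise". It also says: "All data will also be listed".

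Section 3.4.2 summarises the secondary endpoints descriptively in the mITT Population. It adds tables by syndrome and disease type, by number of doses, and for all transplanted patients whatever their dose count. It names no table by group.

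**The concern.** The objectives ask two questions, one per management strategy, and the design randomises within each strategy so that both can be answered. Read in the most natural way, the analysis text answers neither. It gives one HB-101 versus placebo summary over both strategies.

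Three things are at stake.

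- **Interpretation.** DNAemia and treatment-dose anti-viral use arise differently in patients who are monitored and in patients on 3 to 6 months of prophylaxis. A combined incidence, median time or mean duration describes neither strategy.
- **Use for Phase 3.** Section 2.2.4 says the data should help determine point estimates with which to design and power Phase 3. A combined estimate is a weighted average whose weights come from this trial's enrolment, so it does not carry over directly to a trial in one strategy.
- **Pre-specification.** If the by-group display is settled only after results are known, it becomes a results-dependent choice. Section 2.2.2 allows sponsor team members to be unblinded to each patient after last dose and transplant, and 4.1 allows an interim analysis at a time the sponsor chooses.

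**Working it through.** **Does any section require the by-group display?** There is no stated figure to reproduce, so this is a check of the text.

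- 3.1.3: the phrase on Groups 1 and 2 can mean both together or each. The next sentence separates only Group 3, which favours one block.
- 3.4.1.1: repeats similar wording for post-transplant adverse events and does not settle it.
- 3.4.1.4: names group as a split for immunogenicity plots, so the SAP can state a group split where it wants one.
- 3.4.2: splits by syndrome/disease type and dose, not by group.
- 3.4 and 3.4.4: subgroup analyses are optional, depend on favourable results, and name neither group nor prevention strategy.
- Listings: on the one-block reading, these are the only place where by-group results are assured.

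**Group sizes at the stated limits** (150 patients, 2.2.4):

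- Group 2: 0.54 × 150 = 81, or 54 HB-101 and 27 placebo
- Group 3: 0.15 × 150 = 22.5
- Group 1: 150 − 81 − 22.5 = 46.5, or 31 HB-101 and 15.5 placebo
- Group 1 share of the block: w = 46.5 / (46.5 + 81) = 46.5 / 127.5 = 0.365

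**Dependence on the mix.** The SAP names no effect measure, so take a risk difference (RD) as illustration: combined RD = w × RD1 + (1 − w) × RD2. The effects and every mix other than the first row are assumed.

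| Group 2 / Group 3, % of total | w | RD1 = 20, RD2 = 0 | RD1 = 20, RD2 = 10 |
|---|---|---|---|
| 54 / 15 (stated limits) | 0.365 | 7.3 | 13.6 |
| 54 / 25 | 0.280 | 5.6 | 12.8 |
| 30 / 15 | 0.647 | 12.9 | 16.5 |

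The other assumed mixes (45/15, 45/25, 30/25) give w = 0.471, 0.400 and 0.600, inside this range.

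**Shift from enrolment to mITT.** The mITT Population requires a transplant and at least 2 doses (3.2.2), both after randomisation. With assumed retention of 90% in Group 1 and 70% in Group 2, w = 41.85 / (41.85 + 56.7) = 0.425. With the rates reversed, w = 32.55 / (32.55 + 72.9) = 0.309.

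**Precision of by-group estimates.** Approximate 95% half-width for a risk difference = 1.96 × √[p(1 − p)(1/n1 + 1/n0)], with p the assumed common event rate. For Group 1 at p = 0.5: 1.96 × √[0.25 × (1/31 + 1/15.5)] = 0.305.

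| Half-width, points | Group 1 (31 : 15.5) | Group 2 (54 : 27) | Combined (85 : 42.5) |
|---|---|---|---|
| p = 0.5, enrolled counts | 30.5 | 23.1 | 18.4 |
| p = 0.5, 80% reach mITT (assumed) | 34.1 | 25.8 | 20.6 |
| p = 0.2, enrolled counts | 24.4 | 18.5 | 14.7 |

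**The case against.** The strongest reply is that this is ambiguous wording and not a decision to combine. If 3.1.3 means each of Groups 1 and 2, its general rule already covers the secondary endpoints in mITT, and 3.4.2 has no need to repeat it. The sentence that separates Group 3 governs which outputs stand apart, not which columns appear inside the Groups 1 and 2 output. Layout is also commonly fixed in table templates, which 4.1 mentions and which are not at hand. All of this stands as a limit on certainty. It does not show that the SAP commits to the two contrasts.

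The illustrations rest mostly on assumptions. Only the 36%/64% split follows from SAP figures, and only if both limits bind. Group 3 at 25% fits less well with the roughly 100 patients exposed in 2.2.4: (2/3) × 112.5 + 37.5 = 112.5, against (2/3) × 127.5 + 22.5 = 107.5 at the 15% minimum. Without that case the first illustration runs from about 7 to 13 points instead of 6 to 13. The SAP also gives no reason for unequal retention: the strategies differ only after transplant, when mITT status is already settled. That scenario shows a possibility, not an expectation.

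Finally, the study is descriptive with no formal testing (3.1.4). Because allocation is 2:1 in both groups, a combined comparison is not confounded by group at randomisation. Both points are right and limit the severity. But in a descriptive study the display is the analysis, and a valid average over strategies is still not the contrast that either objective names. Nothing says that the conditional subgroup clause would govern the by-group display, so the risk of a results-dependent choice is a possibility only.

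**Conclusion.** The concern holds, with medium confidence because 3.1.3 has a second possible reading and the output templates are not available. Followed on its more natural reading, the SAP would show neither of the two placebo-controlled contrasts in 2.1.2. It would give Phase 3 planning an estimate that depends on the mix of strategies. That mix is about one third Group 1 at the stated limits and could lie well to either side. How far the combined figure departs from the group effects depends on how much those effects differ, which is unknown. If the effects are equal, combining costs nothing on the risk-difference scale. The point should be corrected, but it does not invalidate the randomised comparison.

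**What to change.** - In 3.4.2, state that every secondary efficacy endpoint is presented by treatment arm within Group 1 and within Group 2, whatever the results.
- Present any combined Groups 1 and 2 summary in addition, with the number of mITT patients from each group in each arm.
- In 3.1.3, say whether the rule for Groups 1 and 2 means each group or both combined, and align 3.4.1.1 with it.

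The cost is SAP wording and extra table columns, with no new data. The by-group estimates are less precise than the combined one and will be rough inputs to Phase 3 planning. That is the reason to keep the combined summary beside them and not to replace it.

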3.1.4 Hypothesis Testing

There is no formal hypothesis testing for this study. This study is for an initial assessment of the safety and immunogenicity of the vaccine candidate.

3.1.5 Handling of Dropouts and Missing Data

In general, data will be analyzed and presented as observed and will not be imputed for the analysis of efficacy and safety.

In case the start and end dates for adverse events and concomitant medications/procedures are missing or incomplete, the missing component(s) will be assumed as the most conservative value possible. For example, Adverse Events (AEs) with missing start dates, but with stop dates either overlapping into the treatment period or missing, will be counted as treatment-emergent, taking the worst-case approach. When partial dates are present in the data, both a partial start date and/or a partial stop date will be evaluated to determine whether it can be conclusively established that the AE started prior to the start of study treatment or ended prior to the start of study treatment. If the above cannot be conclusively established based on the partial and/or present dates, then the AE will be considered as treatment-emergent. Actual data values as they appear in the original case report forms (CRFs) will be presented in the data listings.

If a medication has incomplete start or stop dates, dates will be imputed to determine whether a medication should be considered prior or concomitant. If a medication start date is incomplete, the first day of the month will be imputed for missing day and January will be imputed for missing month. If a medication stop date is incomplete, the last day of the month will be imputed for missing day and December will be imputed for missing month. Incomplete start and stop dates will be listed as collected without imputation.

3.1.6 *COVID-19 pandemic*

The COVID-19 pandemic may impact the conduct of the study from different aspects including quarantines, site closures, travel limitations, interruptions to the supply chain for the investigational product, or other considerations if site personnel or trial patients become infected with COVID-19. Study procedures affected by the COVID-19 pandemic are recorded, as are reasons for study discontinuation/screen failure, protocol deviations, and adverse events. All such data will be listed, and any summaries of this data are mentioned below.

